### **8.3. Patient Discontinuation and Termination**

Patients have the right to discontinue study drug or withdraw from study follow-up at any time for any reason, without prejudice to their medical care. Furthermore, the investigator may discontinue a patient from study drug. Consultation with the medical monitor should occur. The reason for a patient's discontinuation from study drug or study termination will be recorded in the electronic case report form (eCRF). Any patient who discontinues study drug for 14 consecutive days or more must have approval from the medical monitor prior to resuming treatment with study drug.

#### **8.3.1. Patient Study Drug Discontinuation Criteria**

Study drug discontinuation refers to a patient's stopping administration of study drug. Reasons for study drug discontinuation may include the following:

- ADVERSE EVENT [Occurrence of an AE or change in medical status that will lead the investigator to be concerned about the patient's welfare];
- DEATH;
- LOST TO FOLLOW UP [Patient lost to follow-up];
- NON-COMPLIANCE WITH STUDY DRUG [Subject has not agreed with or not adequately followed the instructions related to the study medication];
- OTHER [Other specified reason for patient discontinuation];
- PHYSICIAN DECISION [Specified medical reason for patient discontinuation];

- PREGNANCY [Females who become pregnant during the study];
- PROTOCOL-SPECIFIED WITHDRAWAL CRITERIA MET [Reached ESKD];
- PROTOCOL DEVIATION [Non-compliance with protocol]
- STUDY TERMINATED BY SPONSOR;
- SITE TERMINATED BY SPONSOR;
- WITHDRAWAL BY SUBJECT.

The temporary discontinuation and reason for discontinuation must be recorded in the eCRF.

Patients who permanently discontinue study drug *prior to the Week 12 study visit* should be brought back to the clinic as soon as possible to complete the procedures associated with the Week 12 visit (i.e., end-of-treatment visit). For patients who permanently discontinue study drug early, and *during a scheduled study visit*, the Week 12 assessments should be completed at that visit.

To minimize missing data in the OT period, all patients who permanently discontinue study drug early should be encouraged to complete all visits and assessments in the OT period, and patients should return to complete the Week 17/EOS visit as outlined in the Schedule of Assessment (see [Table 4](#)) unless, in the rare occurrence, the patient terminates participation in the study. As an example, if drug is permanently discontinued at Week 5, the patient would return as soon as possible for EOT procedures. The date of the patient's last dose would be the start of the OT period, and the patient would complete all OT visits and assessments (OT Days 3, 7, 21, 28, and 35) over the next 5 weeks. At the patient's target Week 17 date (based on date of randomization), the patient should return to the clinic to complete EOS procedures as the final data collection.

### **8.3.2. Patient Study Termination Criteria**

Study termination refers to a patient's stopping all study follow-up, which includes study assessments, visits, and all contact with the site regarding the trial. Reasons for early study termination include the following:

- DEATH;
- LOST TO FOLLOW-UP;
- WITHDRAWAL OF CONSENT BY SUBJECT.

Every reasonable effort should be made to maintain contact with all patients enrolled in the study. If contact is lost, the PI or study personnel should attempt contact with the alternate contacts provided by the patient, the site should attempt to reach the patient through any possible method including phone, email, text, and through a certified letter. Contact must have been attempted by both the PI and the study team, prior to a patient being considered lost to follow up. Patients should not be considered lost to follow-up until the scheduled Week 17/EOS visit date.

The term "withdrawal of consent" should be used only when the patient no longer wishes to participate in the trial and no longer authorizes investigators to make efforts to continue to obtain their outcome data. Unless the patient provides their written withdrawal of consent or there is other written documentation by the investigator confirming the patient's verbal intent to

completely withdraw from the trial, patients should be followed for all protocol specified evaluations and assessments. The investigator should inquire about the reason for withdrawal of consent, request the patient return all unused investigational product, request the patient return for end-of-treatment and follow-up visits (if applicable), and follow-up with the patient regarding any unresolved AEs. Withdrawal of consent is a critical trial event and therefore should be approached with the same degree of importance and care as is used in initially obtaining informed consent. The reasons for a patient's intended withdrawal need to be completely understood, documented and managed to protect the rights of the patient and the integrity of the trial.

If a subject is discontinued early from the study, the date the subject is withdrawn from the study and the reason for withdrawal will be recorded on the eCRF.

In case of discontinuation from study, the EOT visit assessments should be performed, and any unresolved AEs or SAEs will be followed up according to Section [11.2.1.1](#).

Patients who discontinued drug and also choose to terminate participation in the trial should be brought back to the clinic as soon as possible for early termination assessments (i.e., Week 12 end-of-treatment visit).

## 9. TREATMENT OF PATIENTS

### 9.1. Select Management Guidelines

The guidelines below apply to the management of study participants.

#### 9.1.1. Management of Fluid Status

Specific risk mitigations procedures will be employed to reduce the potential for bardoxolone methyl-induced fluid overload. These procedures include exclusion of patients with any severe kidney disease, defined as an eGFR value of  $< 20 \text{ mL/min/1.73 m}^2$ . To exclude patients with significant cardiac dysfunction, the study will exclude patients with a history of clinically significant cardiac disease. Patients who have evidence of volume overload at baseline, defined as BNP level of  $> 200 \text{ pg/mL}$ , will also be excluded.

Laboratory data and rapid weight gain will also be used to monitor fluid status after randomization. Patients who experience a BNP  $> 100 \text{ pg/mL}$  that represents a doubling (or more) of BNP levels from Day 1 should have an unscheduled telephone contact immediately (see Section 9.10.15 for description of telephone contact). In addition, patients will be given a Sponsor-provided scale to use at home to collect and record their weights daily during the first 8 weeks of the treatment period and weekly thereafter. Patients who experience a five-pound (2.3 kilograms) or greater increase in weight since their Day 1 weight during the first 8 weeks must have an unscheduled telephone contact immediately. Whether due to BNP elevations or weight gain, if clinically important fluid retention is suspected, the patient must be instructed to stop taking their study medication immediately and be medically evaluated by the investigator or a local physician within 1 to 2 days.

Investigators are encouraged to consider starting or increasing doses of diuretics (thiazides, loop diuretics) early after recognition of edema. This can be done concurrently with temporary drug discontinuation and re-initiation. Patients may not restart their study medication until the investigator has completed and documented an assessment of fluid overload.

Beyond Week 8, patients who experience a weight increase of five pounds (2.3 kilograms) or greater compared to Day 1 will be instructed to contact the clinic to assess the need for an unscheduled physical examination and laboratory assessment by the investigator. Study medication should not be discontinued unless clinically important fluid retention is suspected. If suspected, the patient must be instructed to stop taking their study medication immediately and be medically evaluated by the investigator or a local physician within 1 to 2 days.

Investigators should advise patients to watch for signs and symptoms of fluid overload. Patients should be informed to notify their physicians immediately if they experience swollen feet, chest pain, shortness of breath with mild exertion or while lying down, or other relevant symptoms.

The investigator must immediately assess symptoms of fluid overload and determine appropriate medical management, as necessary, including whether stopping drug administration is required.

#### 9.1.2. Management of Elevated Aminotransferase Levels (ALT and/or AST)

Nearly all instances of elevated aminotransferases due to bardoxolone methyl treatment are expected to be asymptomatic. Some patients may experience more rapid increases in ALT/AST

values than others during the dose titration period. Investigators may consider extending the time between each dose increase from two weeks to four weeks to manage ALT/AST elevations.

Check aminotransferase levels (as well as TBL, GGT, alkaline phosphatase (ALP), and International Normalized Ratio [INR]) within 72 hours if the following occurs:

- ALT or AST levels  $> 3X$  ULN.

Repeat testing every 72 to 96 hours until aminotransferase levels are below  $3X$  the ULN for at least one week. Patient should be followed until aminotransferase level returns to normal. Testing for patients not located near the investigator (such that it is impractical to return to the site at the required intervals) may be performed at a local lab and sent to the investigator and medical monitor for review, by approval from the medical monitor.

Discontinue study drug administration permanently if any of the following occur:

- ALT or AST  $> 8X$  ULN;
- ALT or AST  $> 5X$  ULN for more than 2 weeks;
- ALT or AST  $> 3X$  ULN and (TBL  $> 2X$  ULN **or** INR  $> 1.5$ );
- ALT or AST  $> 3X$  ULN with the appearance of fatigue, nausea, vomiting, right upper quadrant pain or tenderness, fever, rash, and/or eosinophilia ( $> 5\%$ ).

The hepatobiliary tree must be visualized (e.g., ultrasound, magnetic resonance imaging [MRI]) and assessed if a patient discontinues taking study drug secondary to elevated transaminase levels. Additional tests and imaging may be warranted depending on the clinical presentation.

### **9.1.3. Management of Muscle Spasms**

Basic symptomatic relief is the first step in managing muscle spasm, including walking, adequate hydration, wearing socks, and stretching before bedtime. Assessment of levels of electrolytes such as magnesium, calcium, and potassium may indicate the need for replacement. Serum vitamin D levels may be collected by the investigator, in the evaluation of muscle spasms. If vitamin D levels are low, supplementation may be warranted. Muscle relaxants may also help relieve symptoms.

### **9.1.4. Weight Loss**

Ongoing assessments to ensure that the patient is receiving adequate nutrition and consideration of other etiologies of weight loss may be warranted for patients receiving bardoxolone methyl.

### **9.1.5. Hypomagnesemia**

In instances where a patient experiences hypomagnesemia, defined as serum magnesium less than 1.3 mEq/L (0.65 mmol/L), consideration should be given to repletion of serum magnesium.

### **9.1.6. Management of Urinary Protein**

Although increases in urinary protein with bardoxolone methyl have not been associated with kidney injury or loss of kidney function, investigators should closely monitor patients if urinary albumin to creatinine ratios increase by more than 100% and exceed 1000 mg/g for proteinuria and should consult the medical monitor for appropriate measures.

### **9.1.7. Management of Blood Pressure**

Investigators should attempt to maintain the blood pressure within the range recommended by the Kidney Disease Blood Pressure Working Group :  $\leq 140$  mmHg systolic and  $\leq 90$  mmHg diastolic for patients with UACR  $< 30$  mg/g, and  $\leq 130$  mmHg systolic and  $\leq 80$  mmHg diastolic for patients with UACR  $> 30$  mg/g ([KDIGO, 2012](#)).

Patients being treated with an ACEi and/or ARB should be receiving the maximally tolerated labeled daily dose (MTLDD), defined as the dose at or below the labeled dose that does not exhibit any intolerable adverse effects (e.g., hypotension, hyperkalemia), based on the investigator's assessment. If the patient is currently receiving one drug (ACEi or ARB) below the maximum labeled dose, the drug should be titrated to the MTLDD based on the assessment of tolerability by the investigator at least 6 weeks prior to the Screen A visit.

Diuretics may be titrated to help maintain blood pressure target levels.

Any changes in ACEi or ARB use or diuretic therapy should be preceded by consideration of any relevant contraindications as per the local product information.

### **9.1.8. Nausea**

Nausea may occur with higher doses of bardoxolone methyl. Nausea AEs are typically mild and reversible within a few weeks after treatment initiation. If symptoms do not resolve, dose de-escalation, with consultation of the medical monitor, may be reasonable.

### **9.1.9. End Stage Kidney Disease**

Patients approaching ESKD should be closely monitored by the investigator to fully characterize their progression. For patients with eGFR  $\leq 15.0$  mL/min/1.73 m^2, initiate more frequent follow-up to closely monitor safety assessments (i.e., clinical chemistry (incl. eGFR), hematology, vital sign assessments (incl. weight), BNP and NT-proBNP). Similar frequent follow-up may also be implemented for patients with eGFR  $> 15.0$  mL/min/1.73 m^2 who, in the investigator's opinion based on the anticipated progression of their disease, may be approaching ESKD. Patient follow-up should be at least once every 4 weeks ( $\pm 2$  weeks), until one of the following occurs:

- Initiation of dialysis;
- Receipt of transplant.

If a patient will imminently initiate dialysis or receive a transplant, the patient should be brought in for an EOT visit in order to have EOT/Week 12 assessments conducted, if at all possible (prior to ESKD date).

Upon initiation of dialysis or receipt of kidney transplant, study drug should be permanently discontinued. Following permanent study drug discontinuation due to initiation of dialysis or receipt of kidney transplant, patients should continue to be followed only for vital status and SAEs by phone or in person according to the planned contact schedule in Section [7.6](#) through their scheduled Week 17 visit date. See Section [8.3](#) for procedures following permanent study drug discontinuation. Initiation of dialysis and receipt of kidney transplant due ESKD should be considered important medical events, and as such recorded as SAEs.

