## 8.2. Subject Exclusion Criteria

All patients with any of the following conditions or characteristics must be excluded from the study:

1. Prior exposure to bardoxolone methyl;
2. CKD secondary to or associated with any of the following:
  - a. History of rapidly progressive glomerulonephritis (RPGN)
  - b. Glomerulonephritis requiring immunosuppression in the 6 months prior to Screen A
3. Concomitant use of tolvaptan. Patients previously treated with tolvaptan must have discontinued drug for at least 3 months prior to Screen A visit;
4. Patients treated with polycystic kidney disease-modifying agents (somatostatin analogues) within 3 months prior to the Screen A visit;
5. Systemic immunosuppression for more than 2 weeks, cumulatively, within the 12 weeks prior to Day 1 or anticipated need for immunosuppression during the study;
6. Patients currently taking a sodium/glucose cotransporter-2 inhibitor (SGLT2i), requiring dose adjustments within 12 weeks prior to Day 1 or if dose is anticipated to change during study participation;
7. B-type natriuretic peptide (BNP) level > 200 pg/mL at Screen A visit;
8. Uncontrolled diabetes (HbA1c > 11.0%) at Screen A visit;
9. Serum albumin < 3 g/dL at Screen A visit;
10. Kidney or any other solid organ transplant recipient or a planned transplant during the study;
11. Acute dialysis or acute kidney injury within 12 weeks prior to Screen A visit or during Screening;
12. History of clinically significant cardiac disease, including but not limited to any of the following:
  - a. Clinically significant congenital or acquired valvular disease
  - b. Left ventricular ejection fraction < 40% (based on historical echocardiogram)
  - c. History of hospitalization for heart failure within 12 months prior to Screen A
  - d. New York Heart Association Class III or IV congestive heart failure (CHF)
  - e. Symptomatic coronary disease (prior myocardial infarction, percutaneous coronary intervention, coronary artery bypass graft surgery, or unstable angina) within 12 months prior to Screen A
  - f. Pericardial constriction (based on historical echocardiogram)
  - g. Restrictive or congestive cardiomyopathy (based on historical echocardiogram)
  - h. Uncontrolled atrial fibrillation

- i. History of unstable arrhythmias;
13. Systolic blood pressure < 90 mm Hg at Screen A visit after a period of rest;
14. Body mass index < 18.5 kg/m^2 at the Screen A visit;

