## **11.6. Recording Adverse Events**

All conditions present prior to the administration of the first dose of study drug (Day 1) should be documented as medical history. After the first dose, documentation of AEs shall continue until the last study follow-up visit, regardless of the relationship of the AE to study drug.

Information to be collected includes type of event, date of onset, date of resolution, investigator-specified assessment of severity and relationship to study drug, seriousness, as well as any action taken.

While an AE is ongoing, changes in the severity (e.g., worsening and improving) should be noted in the source documents, but when documenting the AE, only the total duration and greatest severity should be recorded in the eCRF. AEs characterized as intermittent require documentation of onset and duration.

All drug-related (possibly, probably, or definitely related, see Section 11.4) AEs and abnormal laboratory test results reported or observed during the study must be followed to resolution (either return to baseline or within normal limits). All other AEs will be followed through the final visit indicated in [Table 4](#), as appropriate.

AEs resulting from concurrent illnesses, reactions to concurrent illnesses, reactions to concurrent medications, or progression of disease states must also be reported. Preexisting conditions (present before the start of the AE collection period) are considered concurrent medical conditions and should NOT be recorded as AEs. However, if the patient experiences a worsening or complication of such a concurrent condition, the worsening or complication should be recorded as an AE. Investigators should ensure that the AE term recorded captures the change in the condition (e.g., "worsening of..."). Any improvement in condition should be documented per Section [9.10.11](#).

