## 5. GENERAL CONSIDERATIONS FOR DATA ANALYSES AND HANDLING

The efficacy and safety analyses use the analysis sets defined in Section 5.3. Patient listings (as appropriate) of all analysis data that support summary tables and/or figures are provided along with their source data. The summary tables do not include measurements from patients excluded from the pre-defined analysis sets or extra measurements, such as values not closest to the target study day unless specified otherwise, but the patient listings do include these data. Missing data are not imputed, unless otherwise specified. In general, patient listings are sorted by patient number and assessment date (time and parameter, as applicable). Any laboratory value (including eGFR), vital sign assessment, or ECG value collected after starting dialysis or after receiving a kidney transplant is considered invalid and will be treated as missing. If a subject has a moderate, severe or serious adverse event of COVID, all safety and efficacy findings except AEs in both the on-treatment and off-treatment periods will not be summarized after the start date of the COVID adverse event start date.

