### 7.2. Statement of the Null and Alternate Hypothesis

The primary efficacy analysis compares the change from baseline in eGFR for patients randomized to bardoxolone methyl ( $\mu$  BARD) to the change from baseline in eGFR for patients randomized to placebo ( $\mu$  placebo) at the endpoint-specified visit according to the following hypotheses:

- Null hypothesis,  $H_0: (\mu \text{ BARD}) - (\mu \text{ placebo}) = 0 \text{ mL/min/1.73 m}^2$
- Alternative hypothesis,  $H_1: (\mu \text{ BARD}) - (\mu \text{ placebo}) \neq 0 \text{ mL/min/1.73 m}^2$

Because eGFR decreases with disease progression, an increase in eGFR relative to placebo is considered evidence of benefit.

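### SAP Section 5 sets all laboratory values, vital signs and ECGs after any dialysis to missing, even after recovery, and no planned analysis counts kidney failure as an unfavourable outcome

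*Protocol*

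**What the plan says.** **Protocol 9.1.9 (End Stage Kidney Disease).** "Upon initiation of dialysis or receipt of kidney transplant, study drug should be permanently discontinued". After that, "patients should continue to be followed only for vital status and SAEs by phone or in person", up to the scheduled Week 17 date. The section also asks for closer monitoring once eGFR is 15.0 or lower, for an end-of-treatment visit before dialysis where possible, and for dialysis or transplant due to end-stage disease to be recorded as an SAE. It refers the reader to Section 8.3 for follow-up.

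**SAP Section 5.** "Any laboratory value (including eGFR), vital sign assessment, or ECG value collected after starting dialysis or after receiving a kidney transplant is considered invalid", and such a value "is considered invalid and will be treated as missing". The sentence has no qualifier for duration, chronicity or recovery. Adverse events and deaths are not in its list.

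**Handling of the gap.** SAP 5.6.1.1 imputes nothing for the primary MMRM. The two sensitivity analyses of the primary endpoint are an ANCOVA on observed Week 12 values (7.4.1.1) and an ANCOVA after multiple imputation within treatment group under missing at random (7.4.1.2 with 5.6.1.2).

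**Related text.**
- SAP 7.4.1 says that the Week 12 analysis uses available eGFR whether or not the patient is still taking study drug.
- SAP 7.2: "Because eGFR decreases with disease progression, an increase in eGFR relative to placebo is considered evidence of benefit".
- Exclusion criterion 11 in Protocol 8.2 names temporary dialysis as its own concept: "Acute dialysis or acute kidney injury within 12 weeks prior to Screen A visit or during Screening".
- Protocol 11.6: "documentation of AEs shall continue until the last study follow-up visit".
- Protocol 8.3.1 asks that all early discontinuers be encouraged to complete the off-treatment and Week 17 visits.

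**The concern.** There are two separate problems.

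1. **The trigger is too wide.** An eGFR taken during dialysis does not measure the patient's own kidney function, so discarding it is right. The SAP, however, discards everything from the start of dialysis onward. A patient whose dialysis ends and whose kidneys recover would have valid eGFR values thrown away, and so would measures that dialysis does not directly affect, such as ALT and AST. The trial's own exclusion criteria show that acute dialysis was recognised as something different.

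2. **The outcome has no place in the efficacy analysis.** In end-stage disease the value is missing because the kidney failed, so the missingness is caused by the outcome. The MMRM predicts the unobserved visits from the patient's earlier values and the arm's mean course. Imputation within arm does much the same, and the observed-case ANCOVA drops the patient. SAP 5.6.1.1 says the sensitivity analyses assess robustness, but none of them varies this assumption.

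Because a higher eGFR is read as benefit, leaving these failures out flatters whichever arm has more of them.

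**Working it through.** **Inputs.** From Protocol 12.1: 35 patients per arm, SD 8, planned difference 5.9, 15% dropout, two-sided 0.05. The documents give no dialysis rate and no eGFR value for a patient with kidney failure. Everything about the event itself is therefore an assumption.

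**The plan's own figure.** Evaluable per arm: 35 × 0.85 = 29.75, about 30. SE = 8 × √(2/30) = 2.07. Power of the two-sample t-test (noncentral t) is 79.9% at 29.75 per arm and 80.2% at 30, so the stated 80% reproduces. Losing one, two or three patients from one arm lowers power from 80.2% to 79.5%, 78.8% or 78.0%. Precision is not the problem; the question is the estimate.

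**Size under the MMRM (assumed scenario).** One bardoxolone patient has baseline eGFR 22 and starts dialysis after Week 6, so Weeks 8 and 12 are missing. The reference is an assigned value of 10, a change of 10 − 22 = −12. The Week 12 values the model credits come from a small simulation: six visits, unstructured covariance, within-patient correlation 0.6 to 0.9 at 6 weeks, 30 replicates per scenario.

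Shift in the treatment difference = (credited change − assigned change) / 30.

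| Course before dialysis | Credited Week 12 eGFR | Credited change | Gap to −12 | Shift |
|---|---|---|---|---|
| Gradual decline | 14 to 18 | −8 to −4 | 4 to 8 | 0.13 to 0.27 |
| Abrupt event | 21 to 24 | −1 to +2 | 11 to 14 | 0.37 to 0.47 |

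The simulated shifts were 0.1 to 0.45 per event, which agrees. Relative to the SE this is 0.13/2.07 = 6% to 0.47/2.07 = 23%. Relative to 5.9 it is 2% to 8%.

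**Size under the observed-case ANCOVA.** Here the patient simply drops out. With the rest of the bardoxolone arm at 5.9 and placebo at 0, the shift is (5.9 − V)/30, where V is the assumed unfavourable change:
- V = −10: 15.9/30 = 0.53
- V = −12: 17.9/30 = 0.60
- V = −20: 25.9/30 = 0.86

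The MMRM figures are lower because falling values before dialysis stay in the model. An event on placebo moves the difference the other way.

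**Reach of the trigger.** Suppose temporary dialysis starts on Day 21 (assumed). In SAP Table 3 the Week 4 window opens on Day 22 and the Week 12 window closes on Day 98. Any eGFR in the windows for Weeks 4, 6, 8 and 12, and in all six off-treatment windows of Table 4, would then be set to missing, even if dialysis had ended within days.

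**The case against.** Several points on the other side stand.

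- **Data are not cut off altogether.** A reader might infer that data collection stops and that all later data are voided. The documents do not say so: vital status and SAEs continue to the Week 17 date, and the SAP rule covers laboratory values, vital signs and ECGs only.
- **Kidney failure is not invisible.** A reader might also infer that such a patient is scored as having a healthy kidney. eGFR before dialysis stays in the MMRM, and a pre-dialysis visit is requested, though it counts as Week 12 only on Days 71 to 98. In the gradual scenario the model credits 14 to 18 from a baseline of 22, which is a marked loss.
- **Events are probably rare.** Entry requires eGFR of at least 20, and planned transplant and recent acute dialysis are excluded. Protocol 11.7 describes dialysis for end-stage disease as common in this population, but only to justify a reporting exemption, and it gives no rate over 12 weeks.
- **The Protocol is not clearly at fault on temporary dialysis.** Section 9.1.9 is headed End Stage Kidney Disease and its SAE sentence is limited to that condition. The missing qualifier is an SAP fault.
- **Fewer values may exist to be voided.** If 9.1.9 is applied as written, few later laboratory values are collected. If study drug stopped on Day 21, the off-treatment visits would fall on Days 24 to 56 (21 + 3 to 21 + 35), with none in the Week 12 window, although SAP 5.5.3.1 has such patients resume the planned schedule. Footnote d of SAP Table 3 may also exclude values taken off drug, which itself conflicts with 7.4.1. On-treatment safety tables end with treatment (SAP 5.5.3), so the safety loss falls mainly on off-treatment tables and those covering any time in the study.
- **Counts are partly available already.** Serious TEAEs by treatment and reasons for stopping treatment are tabulated, and reaching end-stage disease is a listed reason.
- **Dialysis alters more than creatinine.** BUN, electrolytes and weight change with it, so restoring every other measure would be wrong.

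These points limit the size and reach of the concern. They do not supply the missing qualifier or a planned check on the ignorability assumption.

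**Conclusion.** The concern holds in a limited form. The SAP rule is too broad as worded, because it can discard valid eGFR after recovery and so departs from the approach in SAP 7.4.1. Separately, no planned analysis of the primary endpoint treats end-stage kidney disease as an unfavourable outcome, although missingness there is caused by the outcome.

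The likely effect on the primary estimate is small: about 0.1 to 0.5 mL/min/1.73 m² per event confined to one arm, against an SE of about 2.07. This rests on an assumed baseline of 22, an assigned value of 10, dialysis after Week 6, assumed correlations, and about 30 evaluable patients per arm. The number of events is unknown.

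The documents do not support reading this as invalidating the primary analysis or as biased toward bardoxolone in particular. The direction depends on which arm has more events. The differing follow-up instructions in Protocol 9.1.9, 8.3.1 and 11.6 are a matter for reconciliation, not an analysis error.

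**What to change.** 1. **SAP Section 5.** Apply the rule to eGFR, creatinine and other measures that dialysis directly alters, after chronic dialysis or transplant. For temporary dialysis, void those measures only while dialysis continues. Keep any collected measures that dialysis does not directly affect, such as ALT and AST, in the safety summaries, and list the rest with a flag.
2. **SAP 7.4.1.2.** Add a sensitivity analysis that gives every visit after end-stage kidney disease the same prespecified unfavourable eGFR value in both arms. Show the number of such events by arm beside the Week 12 result.
3. **Protocol 9.1.9.** Reconcile its follow-up wording with 8.3.1 and 11.6, so that sites know which visits and which adverse events to record after dialysis or transplant.

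The cost is some SAP wording, one additional analysis and one protocol clarification. The primary model is unchanged. The drawback is that the assigned value is a convention, which is why it belongs in a sensitivity analysis only. Items 1 and 2 should be settled before unblinding, in line with SAP 1.2.
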